2.3. Study Plan

After a screening period of up to 28 days, Group 1 and Group 2 patients will receive up to twelve 56-day (8-week) treatment cycles for a total of up to 96 weeks of treatment. Each patient will receive 3 mg/kg cemiplimab intravenously on days 1, 15±3, 29±3, and 43±3 during each treatment cycle. Tumor assessments will be made at the end of each treatment cycle. Extensive safety evaluations will occur on day 1 of each cycle; routine safety evaluations will be conducted at each cemiplimab dosing visit.

Group 3 patients will receive up to six 63-day (9-week) treatment cycles for up to 54 weeks of treatment. Each patient will receive 350 mg cemiplimab intravenously on days 1, 22±3, and

43 ±3 during each treatment cycle. Tumor assessments will be made at the end of each treatment cycle. Extensive safety evaluations will occur on day 1 of each cycle, with routine safety evaluations to be conducted at each cemiplimab dosing visit.

Group 4 patients will receive up to six 56-day (8-week) treatment cycles for up to 48 weeks of treatment. Each patient will receive 600 mg cemiplimab intravenously on day 1, 29±3, and 56 ±3 during each treatment cycle. Tumor assessments will be made at the end of each treatment cycle. Extensive safety evaluations will occur on day 1 of each cycle, with routine safety evaluations to be conducted at each cemiplimab dosing visit.

Group 5 patients will receive up to six 63-day (9-week) treatment cycles for up to 54 weeks of treatment. Each patient will receive 438 mg cemiplimab SC for the first dose and receive 350 mg cemiplimab intravenously on day 22±3, and 43 ±3 in cycle 1 and day 1, 22±3, and 43 ±3 during rest of treatment cycles. Tumor assessments will be made at the end of each treatment cycle. Extensive safety evaluations will occur on day 1 of each cycle, with routine safety evaluations to be conducted at each cemiplimab dosing visit.

Group 6 patients will receive up to twelve 63-day (9-week) treatment cycles for up to 108 weeks of treatment. Each patient will receive 350 mg cemiplimab intravenously on days 1, 22±3, and 43 ±3 during each treatment cycle. Tumor assessments will be made at the end of each treatment cycle. Extensive safety evaluations will occur on day 1 of each cycle, with routine safety evaluations to be conducted at each cemiplimab dosing visit. After implementation of PA9, patients will be given the option to receive subsequent doses of cemiplimab SC. The first 12 patients who opt to switch to SC will receive cemiplimab [REDACTED]. The next ≥6 patients who opt to switch to SC will receive cemiplimab [REDACTED]. Group 6 patients will have the option to switch to SC dosing or to remain on 350 mg Q3W IV dosing.

A patient will receive treatment until the treatment period (96 weeks in Group 1 and Group 2; 54 weeks in Group 3; 48 weeks in Group 4; 54 weeks in Group 5; 108 weeks in Group 6) is complete, or until disease progression, unacceptable toxicity, withdrawal of consent, or confirmed complete response (CR). Group 1 and Group 2 patients with confirmed CR after a minimum of 48 weeks of treatment and Group 6 patients with confirmed CR after a minimum 54 weeks of treatment may elect to discontinue treatment and continue with all relevant study assessments (eg, efficacy assessments).

Groups 1 through 5: Patients in all groups who do not experience progressive disease (PD) will be followed for an additional nontreatment period of up to approximately 6 months with scans performed every 8-12 weeks. After completion of this follow-up period, patients will then enter an extended follow-up period for approximately 1 additional year with assessments every 4 months. Patients in Groups 1 to 5 who complete treatment without disease progression and subsequently experience disease progression during the follow-up period without any intervening systemic anticancer therapy, are eligible for up to 2 years of retreatment with cemiplimab 350 mg IV Q3W.

Group 6: Patients who do not experience PD at the completion of the planned treatment period will enter follow-up for approximately 6 months. There is no extended follow-up for Group 6. Patients enrolled in Group 6 are not eligible for retreatment.

3. ANALYSIS POPULATIONS

In accordance with guidance from the International Conference of Harmonization of Technical Requirements for Registration of Pharmaceuticals for Human Use (ICH) guideline ICH E9 Statistical Principles for Clinical Trials (ICH, 1998), the following population sets will be used for statistical analysis. A patient is deemed eligible and enrolled after the patient completes the screening process and the investigator deems that the subject is eligible, and the investigator orders study drug in interactive web response system (IWRS). At that point, the patient's status in IWRS changes from "in screening" to "enrolled." A patient is not deemed eligible until he/she is enrolled in IWRS.

3.1. Full Analysis Set (FAS)

The full analysis set (FAS) includes all patients who have passed screening and deemed to be eligible for this study. All efficacy endpoints will be analyzed using FAS.

3.2. Safety Analysis Set (SAF)

The safety analysis set (SAF) includes all enrolled patients who received any study drug for each group. Treatment compliance/administration and all clinical safety variables will be analyzed or summarized using the SAF.

3.3. Pharmacokinetic Analysis Set

The PK analysis set for cemiplimab will include all patients who had received cemiplimab/ and had at least 1 qualified (non-missing) postbaseline measurement of cemiplimab concentration in serum.

3.4. Anti-drug Antibody Set

The ADA population for cemiplimab includes all treated patients who had at least 1 postdose ADA result for cemiplimab.

3.5. Biomarker Analysis Set

The biomarker analysis set (BAS) includes all treated patients who had at least 1 sample assayed.

4. ANALYSIS VARIABLES

4.1. Demographic and Baseline Characteristics

The following demographic and baseline characteristics variables will be summarized:

- Age at screening in years (quantitative and qualitative variable: <65, ≥65 years)
- Sex (Male, Female)
- Race (American Indian/Alaskan Native, Asian, Black/African American, Native Hawaiian/Other Pacific Islander, White and Other)
- Ethnicity (Hispanic/Latino or not)
- Weight (kg)
- Height (cm)
- Body mass index (BMI) calculated from weight and height: $\text{weight (kg)} / [\text{height (m)}]^2$
- ECOG performance status (0, 1)
- For group 1 and group 3, type metastatic disease (Distant or Nodal only).

4.2. Medical History

Medical history will be coded to a Preferred Term (PT) and associated primary System Organ Class (SOC) according to the latest available version of MedDRA.

Oncology history:

- Primary diagnosis
- Time from initial diagnosis to study entry
- Histologic grade
- Cancer stages at initial diagnosis and at screening
- Prior anticancer systemic therapy
- Prior radiotherapy
- Duration of latest anticancer systemic therapy

4.3. Pre-Treatment / Concomitant Medication

Medications/Procedures will be recorded from the day of informed consent until the end of study (EOS) visit. Medications will be coded to the anatomical therapeutic chemical (ATC) level 2 (therapeutic main group) and ATC level 4 (chemical/therapeutic subgroup), according to the latest available version of WHO Drug Dictionary (WHODD). Patients will be counted once in all ATC categories linked to the medication.

Pre-treatment medications/procedures: medications taken or procedures performed prior to administration of the study drug, particularly, prior cancer related surgery, prior cancer related radiotherapy, and prior cancer related systemic therapy: chemotherapy, targeted therapy, immunotherapy and others.

Concomitant medications/procedures: any treatment administered from the time of informed consent until 30 days after the last study treatment will be considered concomitant treatment. This includes medications and other therapies for which administration started before the study and will continue during the study, as well as any therapies started in the 6-month follow-up period to treat a study drug related AE. All concomitant treatments must be recorded in the study case report form (CRF) with the generic name, dose, dose unit, frequency, indication, and start/stop date, as appropriate.

4.4. Rescue Medication/Prohibited Medication

While participating in this study, a patient may not receive any standard or investigational agent for treatment of a tumor other than cemiplimab as monotherapy. Any other medication which is considered necessary for the patient's welfare, and which is not expected to interfere with the evaluation of the study drug, may be given at the discretion of the investigator.

Patients using immunosuppressive doses (>10 mg per day of prednisone or equivalent) of systemic corticosteroids other than for corticosteroid replacement will not be eligible for the study. It is recommended that patients do not receive systemic corticosteroids such as hydrocortisone, prednisone, prednisolone (Solu-Medrol®) or dexamethasone (Decadron®) at any time throughout the study except in the case of a life-threatening emergency and/or to treat an immune-related adverse event (irAE). Physiologic replacement doses of systemic corticosteroids are permitted, even if >10 mg/day prednisone equivalents. A brief course of corticosteroids for prophylaxis (eg, contrast dye allergy) or for treatment of non-autoimmune conditions (eg, delayed-type hypersensitivity reaction caused by contact allergen) is permitted.

4.5. Efficacy Variable

4.5.1. Primary Efficacy Variable

Overall response is based on **central-reviewed evaluation** at each time point at which a response assessment occurs using the RECIST version 1.1 (Appendix 1 of the protocol) or the composite response criteria (Appendix 2 of the protocol).

Best overall response (BOR) is determined once all the overall response data for the patient are known. The best overall response is the best response recorded during the study.

- Best overall response of CR or PR must be confirmed by consecutive evaluations of overall response of CR or PR at time points at least 4 weeks apart. In addition, locally advanced CSCC patients followed by digital medical photography require biopsy to confirm CR.
- Best overall response of SD must have met the response SD criteria at least once ≥ 39 days (6 weeks*7 days/week -3 days) after start of study treatment. Best overall

response of (early) PD does not require confirmation using the RECIST or the composite response criteria.

- The best overall response for patients who do not have any post-baseline tumor assessment will be not evaluable (NE). Patients with best overall response of NE will be considered as not reaching an objective response of CR or PR.

Objective response rate (ORR) is determined by the proportion of patients with best overall response of CR or PR in the FAS by group.

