To account for the possibility of unconventional immune responses, immune-related response criteria (irRC) ([Nishino 2013](#)) can inform the decision regarding whether to continue treatment for an individual patient if the investigator believes it is in the best clinical interest of the patient, **after discussion and approval from the medical monitor**. Reasons for any such decision to treat beyond the protocol definitions of progression **must be documented in the CRFs**. However, irRC are currently deemed a surrogate endpoint ([Postow 2015](#)), and irRC data are not included in the primary endpoint of this study. Any patient who experiences best response (PR or CR) after initial progression (per [Appendix 1](#) or [Appendix 2](#), as appropriate) in the context of continued treatment (according to principles of irRC in after sponsor approval) will not have that best response (partial or complete) counted towards the primary endpoint of this study.

Patients with metastatic CSCC will generally be followed by RECIST 1.1 criteria ([Appendix 1](#)). It is possible that some patients may also have externally visible lesions that are measurable by digital medical photography. Generally, it will be clinically appropriate to follow these externally visible lesions as non-targets. However, patients with externally visible lesions that are deemed clinically significant by the investigator, the clinical and composite response criteria in [Appendix 2](#) may be used in selected cases. However, it is anticipated that most patients in Groups 1 and 3 (and most metastatic patients in Groups 4, 5, and 6) will be followed by RECIST 1.1 only.

For Group 2, response assessment is according to the clinical and composite response criteria in [Appendix 2](#).

For externally visible lesions that are indeterminate-appearing regarding presence of CSCC, see [Appendix 5](#) for guidelines on tumor biopsies. Annotation of tumor measurements and biopsies should adhere to the guidelines in [Appendix 5](#). If annotation of the full perimeter of a lesion is deemed not clinically appropriate by the investigator (eg, an ulcerated lesion), the priority annotation will be the axes delimiters. The perimeter of the lesion should be annotated as fully as possible without causing undue discomfort to the patient.

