8.2. Primary and Secondary Endpoints

8.2.1. Primary Efficacy Endpoints

The primary efficacy endpoint for this study is ORR according to central review during the 12 treatment cycles (Groups 1, 2, and 6), or 6 treatment cycles (Groups 3 and 4). Overall response rate will be assessed separately for patients with metastatic CSCC or locally advanced CSCC:

- For patients with metastatic disease, RECIST version 1.1 will be used to determine ORR ([Eisenhauer 2009](#)) ([Appendix 1](#)). Patients in which all response assessments are performed on radiologic scans according to RECIST 1.1, the determination of the independent radiologic response assessment committee will serve as the central response assessment. Clinical or composite response criteria ([Appendix 2](#)) may be used for patients with externally visible target lesions, if all metastatic lesions are not measurable by RECIST (such as may occur in patients with bone-only metastases).
- For patients with unresectable locally advanced disease, clinical response criteria ([Appendix 1](#)) will be used to determine ORR, for externally visible tumor(s) use bi-dimensional measurements according to World Health Organization (WHO) criteria. Composite response criteria will be used for patients who have both target lesions measurable by clinical response criteria and by RECIST 1.1 to determine ORR ([Appendix 2](#)). In patients achieving a CR, tumor biopsies will be used in the final determination of complete versus PR.

Patients who are deemed not evaluable (NE) by RECIST version 1.1 (Groups 1, 3, 4, and 6; [Appendix 1](#)) or inevaluable by the clinical or composite response criteria (Group 2; [Appendix 2](#)) will be considered as not reaching PR/CR for ORR. ORR will be calculated from time of enrollment.

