The best overall response is the best response recorded from the start of the treatment until disease progression/recurrence (taking as reference for progressive disease the smallest measurements recorded since the treatment started). The patient’s best response assignment will depend on the achievement of both measurement and confirmation criteria. Revised Response Evaluation Criteria in Solid Tumors (RECIST) Version 1.1 ([Eisenhauer 2009](#)) are summarized in the table:

**Response According to Revised Response Evaluation Criteria in Solid Tumors
(Version 1.1)**

Target Lesions	Non-Target Lesions	New Lesions	Overall Response	Best Overall Response when Confirmation is Required ^a
CR	CR	No	CR	≥4 weeks confirmation
CR	Non-CR/Non-PD	No	PR	≥4 weeks confirmation
CR	Not evaluated	No	PR	
PR	Non-CR/Non-PD/not evaluated	No	PR	
SD	Non-CR/Non-PD/not evaluated	No	SD	Documented at least once ≥4 weeks from baseline
PD	Any	Yes or No	PD	no prior SD, PR or CR
Any	PD*	Yes or No	PD	
Any	Any	Yes	PD	

CR=complete response; PD=progressive disease; PR=partial response; SD=stable disease.

^a In exceptional circumstances, unequivocal progression in non-target lesions may be accepted as PD.

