APPENDIX 10. STATISTICAL ANALYSES

ESTIMANDS

For Group 6 primary analysis, the statistical methods for the primary and secondary endpoints will be consistent with that which was done for Groups 1 to 3. This will facilitate a meaningful comparison of Group 6 with the previous groups. Additional statistical analyses will also be performed, including sensitivity analyses for DOR and PFS assuming informative censoring for intercurrent event.

Attributes for ORR per Central Review and Investigator Assessment

1. The study population is defined as CSCC patients who are enrolled on the protocol.
2. The endpoint is ORR, defined as the proportion of patients with BOR of CR or PR. ORR per central review is the primary endpoint, and ORR per investigator assessment is a secondary endpoint.
3. Intercurrent events and how to account for these events are described in [Table 16](#).
4. Estimated ORR will be provided, along with the 2-sided 95% exact binomial confidence interval using the Clopper-Pearson method.

Table 16: Intercurrent Events for Analysis of ORR per Central Review and Investigator Assessment

Intercurrent events	Rules of imputing data in primary analysis
Initiation of palliative radiation therapy	Patient will be considered to have PD at time of initiation of radiation (Section 5.7.4 of protocol).
Surgical removal of target lesion	BOR will be considered as PR if no prior PD is observed (Section 5.7.3 of protocol).
Unconventional responses (eg, a patient first experience PD and then CR or PR)	BOR will be considered as PD.
No evaluable postbaseline tumor assessment	BOR will be deemed NE. Patient with BOR of NE will be included in the ORR analysis as a non-responder.

A sensitivity analysis will be performed for ORR where the intercurrent events of “initiation of palliative radiation therapy” and “surgical removal of target lesion” will be ignored. Patients with unconventional responses will be considered as responders. Patients with BOR of NE will be excluded from this analysis.

Attributes for DOR per Central Review and Investigator Assessment

1. The study population is defined as CSCC patients who are enrolled on the protocol and had a CR/PR response.
2. The endpoint is DOR, measured from the time measurement criteria are first met for CR/PR (whichever is first recorded) until the first date of recurrent or progressive disease or death due to any cause in patients with BOR of CR or PR.

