For Group 6, the rates of intercurrent events are expected to be similar to those observed in Groups 1 to 3. Frequencies of these events in Groups 1 to 3 are presented in [Table 20](#).

Table 20: Frequency of Intercurrent Events in Group 1, 2, and 3 in the Primary Analysis

Intercurrent event	Endpoint	Group 1 (N=59)	Group 2 (N=78)	Group 3 (N=56)
Initiation of radiation therapy	ORR, DOR, PFS	0	0	0
Surgical removal of target lesion	ORR, DOR	1 (1.7%)	0	0
Unconventional response	ORR, DOR, PFS	0	2 (2.6%)	0
No evaluable post-baseline tumor assessment (BOR=NE)	ORR, DOR	7 (11.9%)	7 (9.0%)	6 (10.7%)
Due to early death	PFS	3 (5.1%)	1 (1.3%)	3 (5.4%)
Due to reasons other than death	PFS	4 (6.8%)	6 (7.7%)	3 (5.4%)
Lost to follow-up or Discontinuation of study in patients with BOR of CR or PR	DOR	1 (1.7%)	11 (14.1%)	1 (1.8%)
Due to AE or PD	DOR	1 (1.7%)	1 (1.3%)	0

Intercurrent event	Endpoint	Group 1 (N=59)	Group 2 (N=78)	Group 3 (N=56)
Lost to follow-up or Discontinuation of study after at least one evaluable post-baseline tumor assessment	PFS	15 (25.4%)	35 (44.9%)	19 (33.9%)
Due to AE or PD	PFS	12 (20.3%)	14 (17.9%)	14 (25.0%)
New anti-cancer therapy added	OS	8 (13.6%)	5 (6.4%)	8 (14.3%)
Lost to survival follow up	OS	6 (10.2%)	33 (42.3%)	13 (23.2%)

SUBGROUP ANALYSES – METASTATIC AND LOCALLY ADVANCED CSCC PATIENTS AT FINAL ANALYSIS

Table 21 and Table 22 provide the 95% confidence intervals for observed ORRs for the 2 subgroups of Group 6: metastatic and locally advanced CSCC separately. The primary analysis for Group 6 is based on all advanced CSCC patients, both metastatic and locally advanced. These subgroup analyses are descriptive only.

Table 21: The Binomial Exact Confidence Intervals for Observed ORR in Metastatic CSCC Patients at Final Analysis (N=133)

Number of Responders	ORR (N=133)	95% CI (%)
47	35.3%	(27.3, 44.1)
48	36.1%	(27.9, 44.9)
49	36.8%	(28.6, 45.6)
50	37.6%	(29.3, 46.4)
51	38.3%	(30.1, 47.2)
52	39.1%	(30.8, 47.9)
53	39.8%	(31.5, 48.7)
54	40.6%	(32.2, 49.5)
55	41.4%	(32.9, 50.2)
56	42.1%	(33.6, 51.0)
57	42.9%	(34.3, 51.7)
58	43.6%	(35.0, 52.5)
59	44.4%	(35.8, 53.2)
60	45.1%	(36.5, 54.0)

Table 22: The Binomial Exact Confidence Intervals for Observed ORR in Locally Advanced CSCC Patients at Final Analysis (N=34)

Number of Responders	ORR (N=34)	95% CI (%)
11	32.4%	(17.4, 50.5)
12	35.3%	(19.7, 53.5)
13	38.2%	(22.2, 56.4)
14	41.2%	(24.6, 59.3)
15	44.1%	(27.2, 62.1)

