1.2.4. Modifications from the Statistical Section in the Final Protocol

This study is expected to be a pivotal trial and will be part of the core of the BLA/MAA submission. Accordingly, revision to this plan will only be made if deemed necessary to the furtherance of the trial objectives. Such revision, if necessary, will be completed prior to the final database lock.

Modifications from the Statistical Section in the protocols are listed below:

- Added TTR, DCR, and dDCR as additional analyses.
- Added a sensitivity analysis of ORR using patients who received at least one dose of cemiplimab.

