5. STATISTICAL METHODS

For continuous variables, descriptive statistics will include the following: the number of patients reflected in the calculation (n), mean, median, standard deviation, minimum, and maximum. In addition, 25th percentile and 75th percentile will be provided.

For categorical or ordinal data, frequencies and percentages will be displayed for each category. The denominator will be determined by the analysis population used for the summary.

For time-to-event variables, median time-to-event (and the survival rate at a fixed time point) and its 95% confidence intervals will be summarized by the Kaplan-Meier method.

Statistical analysis for efficacy will be conducted independently for each group.

The data cut-off for primary efficacy analysis will be six months after the last patient starts the treatment, plus at most three additional months if a tumor response of CR or PR occurring at six months need be confirmed. The study will continue for data collection of tumor response, duration of response and safety after primary efficacy analysis. The statistical analysis of duration of response will be updated after four additional months to allow for sufficient data maturation.

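### The SAP's definition of best overall response has no stop at progression or at the end of the planned cycles, so read literally it lets responses the protocol excludes into the primary ORR

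*SAP*

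**What the plan says.** SAP 4.5.1 defines the primary variable. Its window for best overall response (BOR) is: "The best overall response is the best response recorded during the study". A CR or PR must be confirmed at least 4 weeks later, and a CR followed by photography in locally advanced disease needs a biopsy. Neither condition requires that no progression came first. ORR is then the proportion of the full analysis set with BOR of CR or PR.

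The protocol sets a narrower window in four places:

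- **Section 6.3.2.** A patient who responds after initial progression, on continued treatment, "will not have that best response (partial or complete) counted towards the primary endpoint of this study".
- **Section 8.2.1.** The primary endpoint is "ORR according to central review during the 12 treatment cycles (Groups 1, 2, and 6), or 6 treatment cycles (Groups 3 and 4").
- **Appendix 1.** "The best overall response is the best response recorded from the start of the treatment until disease progression/recurrence".
- **Appendix 10, Table 16.** PD followed by CR or PR is scored PD. Only in the sensitivity analysis below that table does the rule reverse: "Patients with unconventional responses will be considered as responders".

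SAP 1.2.4 lists the departures from the protocol's statistical section: three added endpoints (TTR, DCR, dDCR) and one item on ORR, "Added a sensitivity analysis of ORR using patients who received at least one dose of cemiplimab". A change to BOR is not listed.

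**The concern.** The two documents give different windows for the same term, and that term generates the primary endpoint. Followed literally, the SAP sentence makes the protocol's sensitivity rule the primary rule.

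No other part of the SAP supplies the missing stop. Section 5 sets a data cut-off, 5.8.1 censors Group 6 at the first SC dose, and 6.2 deals only with non-evaluable patients. The SAP carries neither Table 16 nor its ORR sensitivity analysis.

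Excluded responses could enter by three routes:

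- response after PD on continued treatment (all groups; protocol 6.3.2);
- first response in cycles 7 to 12 (Groups 3 and 4; protocol 6.3.6);
- response during retreatment after progression (Groups 1 to 5; protocol 6.2.2). Group 6 has no retreatment.

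Each group succeeds if an exact lower confidence limit exceeds a fixed null ORR. The wider window can only add responders, so any error favours success.

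**Working it through.** **Inputs.** Nulls: 25% (Group 2) and 28% (Group 6), protocol 9.1. Sizes: 78 enrolled in Group 2 and 167 planned in Group 6, protocol 4.1. Unconventional responses (PD, then CR or PR), protocol Table 20: Group 1 0/59, Group 2 2/78, Group 3 0/56, pooled 2/193 = 1.0%. For Group 6 the protocol states: "For Group 6, the rates of intercurrent events are expected to be similar to those observed in Groups 1 to 3".

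**Reproducing the plan's rule.** The Clopper-Pearson lower limit for x responders of n is the 0.025 quantile of Beta(x, n − x + 1). For 59/167 it is 28.1%, as in protocol Table 13, and 58/167 gives 27.5%. So 59 is the smallest passing count. It is also the threshold at the alpha-adjusted 95.10% level (lower limit 28.07%; 58 gives 27.5%).

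**What two responders can do.**

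| Group | Null | Responders | Lower 95% limit | Result |
|---|---|---|---|---|
| 2 (N=78) | 25% | 26 | 23.1% | fails |
| 2 | 25% | 27 | 24.2% | fails |
| 2 | 25% | 28 | 25.3% | passes |
| 6 (N=167) | 28% | 57 | 27.0% | fails |
| 6 | 28% | 58 | 27.5% | fails |
| 6 | 28% | 59 | 28.1% | passes |

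**Error at the null.** Let the protocol-defined ORR equal the null p0, and let r be the rate of extra responses admitted. The counted rate is p0 + r(1 − p0) if only non-responders convert, or p0 + r if r is added outright. The one-sided error is P(X ≥ c) for X binomial at that rate, with c = 28 of 78 or 59 of 167.

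| Group | Assumed r | Counted rate | One-sided error |
|---|---|---|---|
| 2 | 0 | 25.0% | 2.1% |
| 2 | 1/78 (one of the two would count) | 26.0–26.3% | 3.4–3.9% |
| 2 | 2/78 | 26.9–27.6% | 5.1–6.7% |
| 6 | 0 | 28.0% | 2.3% |
| 6 | 2/78 × 34/167 = 0.5% (locally advanced share only) | 28.4–28.5% | 3.0–3.3% |
| 6 | 2/193 (pooled) | 28.7–29.0% | 3.8–4.6% |
| 6 | 2/78 in every patient | 29.8–30.6% | 7.3–10.6% |

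The last row is an extreme case and unlikely. It is kept because 0/115 in Groups 1 and 3 together has an upper 95% limit of 3.2%, above 2/78 = 2.6%, so the data do not rule it out. The pooled rate is the one closest to the protocol's own expectation.

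**Not sized.** The documents give no rate for responses in retreatment or for first responses in cycles 7 to 12.

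**The case against.** The best defence is that the protocol already fixes the rule. Section 6.3.2 covers patients assessed under either Appendix 1 or Appendix 2, Table 16 sets BOR to PD, and the silence of SAP 1.2.4 can mean that nothing changed. SAP 4.5.1 also cites Appendix 1. The literal reading even conflicts with SAP 4.5.2: duration of response runs to the first date of progression, so a patient who progressed and then responded would have a negative duration. Table 20 tabulates the two Group 2 cases as intercurrent events in the primary analysis, which suggests that the protocol rule was applied there.

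Much of this stands as evidence of intent. It does not make the sentence correct. The Appendix 1 citation concerns the criteria used at each time point, while the BOR sentence states its own window. Appendix 1 also applies to metastatic disease evaluable by RECIST, and both observed cases were in Group 2, which is locally advanced. Appendix 2 has no BOR window. The negative duration shows that the SAP is internally inconsistent.

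The objection on size is fair. Table 20 does not say that the two responses were confirmed or centrally reviewed, and a rate seen with an active drug need not apply at the null. Two extra responders change the outcome only at 26–27/78 or 57–58/167, which at the design alternatives of 44% and 40% have probability of about 3.8% and 4.3%. Cycles 7 to 12 are open only to patients without PD, so that route concerns the cycle window and not progression. Retreatment needs completed treatment and then progression, so it bears mainly on updates after the primary cut-off. Nothing in the documents shows that an excluded response was ever counted.

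**Conclusion.** The concern holds. The SAP states a BOR window that differs from the protocol's and, if followed, gives a different primary ORR. The likely intent is the protocol rule and the expected numbers are small, so this should be fixed but does not put the design in doubt.

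On the observed frequencies, one-sided error at the null would go from 2.1% to 5.1–6.7% in Group 2 (3.4–3.9% if one of the two cases would count) and from 2.3% to 3.8–4.6% in Group 6 at the pooled rate. This assumes that the Table 20 rates carry over to a true ORR at the null and, apart from the one-case variant, that every such response would be confirmed and accepted centrally. The conflict between the texts does not depend on these assumptions; only the size does.

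**What to change.** Replace the BOR sentence in SAP 4.5.1 with wording to this effect:

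> BOR is the best response first documented from the start of treatment until first documented PD, including events deemed PD under protocol Table 16, within the planned cycles (12 for Groups 1, 2 and 6; 6 for Groups 3 and 4). The confirmatory assessment at least 4 weeks later may fall after the last planned cycle. Assessments during retreatment are excluded. PD followed by CR or PR is scored PD in the primary analysis and as a response only in the protocol's sensitivity analysis.

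Carry Table 16 and its ORR sensitivity analysis into the SAP, and keep the existing censoring at the first SC dose (SAP 5.8.1). The sentence on late confirmation settles a point that protocol 8.2.1 leaves open. It is in the spirit of SAP section 5, which extends the cut-off by "plus at most three additional months if a tumor response of CR or PR occurring at six months need be confirmed".

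Two additions are optional: a window for investigator-assessed ORR in Group 5, which 8.2.1 does not give, and a stop at new systemic anticancer therapy, which is in neither document.

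The cost is SAP wording and one derivation flag. Reported ORR would change only if an excluded response had been counted.
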